
AE	Adverse Event
AR	Adverse Reaction
CF	Consent Form
CI	Chief Investigator
CRF	Case Report Form
CTR	Centre for Trials Research
cv	Curriculum Vitae
DREFAQ	Dresden Falls Questionnaire
FoG	Freezing of Gait
GCP	Good Clinical Practice
ISF	Investigator Site File
ISRCTN	International Standard Randomised Controlled Trial Number
MoCA	Montreal Cognitive Assessment
NHS	National Health Service
OxPAQ	Oxford Participation and Activities Questionnaire
PD	Parkinson's disease
PDQ-8	Parkinson's Disease Questionnaire 8
PI	Principal Investigator
PIC	Participant Identification Centre
PIS	Participant Information Sheet
PROMS	Patient Reported Outcome Measures
QA	Quality Assurance
QC	Quality control
QoL	Quality of Life
RCT	Randomised Controlled Trial
REC	Research Ethics Committee
SAE	Serious Adverse Event
SOP	Standard Operating Procedure
TIDieR	Template for Intervention Description and Replication
тм	Trial Manager
TMF	Trial Master File

TMG	Trial Management Group	
TSC	Trial Steering Committee	
TUG	Timed Up and Go	
UPDRS	Unified PD Rating Scale	

1 Amendment History

The following amendments and/or administrative changes have been made to this protocol since the implementation of the first approved version.

Amendment No.	Protocol version no.	Date issued	Summary of changes made since previous version

2 Synopsis

Short title	Evaluating the feasibility of a samba percussion intervention for people with			
	Parkinson's disease (PD)			
Acronym	SParky Samba			
Funder and ref.	Jacques and Gloria Gossweiler Foundation			
Trial design	Feasibility Randomised Controlled Trial (RCT)			
Trial participants	Patients with Parkinson's disease (PD)			
Planned sample size	Feasibility RCT, n = 60 (30 in intervention group, 30 in activity as usual)			
Planned number of sites	4			
Inclusion criteria	People diagnosed with PD			
	Age 18 or older			
	Able to provide consent to take part			
Exclusion criteria	Has already taken part in a SParky Samba group			
Intervention duration	12 weeks			
Planned trial period	Planned recruitment time from April 2025 – February 2026			
Primary objectives	Determine feasibility of testing the SParky Samba intervention in a feasibility RCT.			
Secondary objectives	Explore the effect of the SParky Samba intervention as compared to activities as usual across function and wellbeing of people with PD.			
Primary outcomes	 Feasibility of participant recruitment and retention and intervention adherence according to pre-specified criteria. 			

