11.3 Adherence

Participants will be emailed a link to the REDCap database each week following the session to complete a self-report attendance checklist.

Group facilitators will also be asked to complete a checklist following each session during the recruitment and intervention delivery period.

12 Trial Procedures

Recruitment and follow-up:

Participants will be identified at clinical sites or via social networks/ word of mouth and eligible participants will be approached and provided with trial information prior to giving informed consent. Participants will be assessed at baseline and at 12 weeks post randomisation following intervention delivery. The intervention delivery period will commence at randomisation (to occur within 2 weeks of baseline assessment) and will last for a period of 12 weeks. With the addition of the process evaluation (see below), participants are expected to be in the trial for no longer than 16 weeks.

Data collection/assessments and blinding

Outcome data will be collected through a combination of patient reported measures completed directly within the database and in person assessments conducted by research staff at site. If a participant choses, they will be able to complete the patient reported outcomes on paper copies if they prefer (see data management section 16.2). participants may be supported with on-line or paper completion at the hospital research visit by the trial research staff, or at home by one of the core trial team members via telephone. Due to the nature of the intervention and the pragmatic design of the trial, researchers collecting assessment data will not be blind to the allocation of participants. In an effort to reduce bias of rating the UPDRS, this assessment will be videoed by the assessor at site and rated independently by an expert blinded to allocation. The measures included in SParky Samba do not form part of routine care, although PD specific measures such as UPDRS and Hoen and Yahr may be used by clinicians ad-hoc as part of their routine assessment of participants at clinic appointments.

Intervention (and intervention comparator) adherence data will be provided through participant self-report and self-report from SParky Samba group facilitators.

Process Evaluation:

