14.1 Randomisation

Participants will be randomised to the intervention or control in a 1:1 ratio, stratified by disease burden (Hoen and Yahr stage). Randomisation will be completed within study REDCap database. Full details of the randomisation procedure will be specified in a separate randomisation plan.

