14.3 Sample Size

As a feasibility study, this has not been powered to detect effects in clinical outcome measures. The recruitment target of 60 has been selected in line with guidance for sample sizes in feasibility studies for 30 participants per group (29). This sample size will allow estimation of recruitment, retention and adherence rates with a 95% binomial confidence interval of no more than plus or minus 13 percentage points irrespective of the point estimate.

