15.1 Main Analysis

Key demographic data will be summarised using descriptive statistics. For feasibility outcomes, recruitment will be assessed as the percentage of eligible people who provide consent to participate in the trial; retention as the percentage of participants recruited who complete the 12-week follow-up assessment; adherence as the percentage of recommended intervention or social control sessions completed. Feasibility criteria will be assessed according to a traffic light system with green (proceed to full effectiveness RCT) if all criteria listed in section 5.3 are in the green zone; amber (requiring adjustment before proceeding to full RCT) if all criteria are either in the amber or green zone; and red (do not progress to full RCT unless major changes are implemented) if at least one criterion is in the red zone. For secondary outcome measures we will calculate descriptive summaries such as mean and standard deviation, and 95% confidence intervals of participants' percentage changes from baseline to 12-week follow-up. This will provide estimates of effect size and variability of drumming-induced changes for use in power calculations for a future RCT.

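### Section 15.1 reads participants' change from baseline as an effect of drumming for powering the next trial, although only a between-arm difference could estimate that effect

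*Protocol*

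**What the plan says.** The Synopsis gives the secondary objective as "Explore the effect of the SParky Samba intervention as compared to activities as usual across function and wellbeing of people with PD". Section 5.2 names the comparator differently but is also comparative. Section 6 describes a parallel-group randomised design with an activity-as-usual control, and section 14.1 adds that allocation is "stratified by disease burden (Hoen and Yahr stage"). Section 4.1 explains that the control is there to separate general social benefit from what is specific to SParky Samba.

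Section 15.1 sets out the analysis of the secondary outcomes: descriptive summaries, with mean and SD as examples, and 95% confidence intervals of participants' percentage change from baseline to 12 weeks. It then states what these are for: "This will provide estimates of effect size and variability of drumming-induced changes for use in power calculations for a future RCT". It names no between-arm difference and does not say that the summaries are by arm.

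On size, section 14.3 says that "this has not been powered to detect effects in clinical outcome measures". On blinding, section 12 says that "researchers collecting assessment data will not be blind to the allocation of participants", and then provides for the UPDRS to be videoed and rated by an expert who is blind to allocation.

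**The concern.** The fault lies in what section 15.1 states, not in what it leaves open. It specifies a summary, gives it a causal meaning and assigns it a use.

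Change from baseline in a treated participant is the sum of any intervention effect and whatever would have happened anyway: disease course, practice on repeated tests such as the MoCA and MiniBEST, regression to the mean, and medication change (the schedule in Figure 3 marks medications at the baseline hospital visit only). The control arm estimates that second part. Unless it is subtracted, the change cannot be attributed to drumming.

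Two things are at stake. The comparative secondary objective has no matching estimate in the analysis section. And the next trial could be planned on a number that is wrong by the amount the control arm changes.

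**Working it through.** **The plan's own figure.** Section 14.3 promises a "95% binomial confidence interval of no more than plus or minus 13 percentage points irrespective of the point estimate". With n = 60 and the worst case p = 0.5, 1.96 × √(0.25/60) = 12.65 points, so the figure reproduces for rates measured in all 60. It concerns feasibility rates and has no bearing on this point. For the clinical outcomes the protocol gives no effect size, SD, correlation or power, so everything below is illustration.

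**Step 1: what each quantity estimates.** Let the mean change be *d* in the intervention arm and *c* in the control arm. The before-after summary estimates *d*. The intervention effect is *d* − *c*. They agree only if *c* = 0.

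**Step 2: effect on a future trial.** Assumptions: SD of change = 1, two-sided 5% level, 90% power, *d* = 0.5.

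- Sizing on *d*: n per arm = 2 × ((1.960 + 1.2816)/0.5)² = 84.06, so 85.
- Power at the true difference: Φ((*d* − *c*) × √(85/2) − 1.960).
- n per arm needed: 2 × ((1.960 + 1.2816)/(*d* − *c*))², rounded up.

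| Control change *c* (SD) | Between-arm effect (SD) | Power with 85 per arm | n per arm needed |
|---|---|---|---|
| 0 | 0.5 | 90% | 85 |
| 0.1 | 0.4 | 74% | 132 |
| 0.2 | 0.3 | 50% | 234 |
| 0.3 | 0.2 | 26% | 526 |
| −0.2 (controls worsen) | 0.7 | 99.5% | 43 |

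For example, at *c* = 0.2: 0.3 × √42.5 − 1.960 = −0.004, and Φ(−0.004) = 0.498.

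**Step 3: other starting values.** With *d* = 0.3 (234 per arm), control changes of 0.1 and 0.2 SD leave 58% and 19% power. With *d* = 0.8 (33 per arm), control changes of 0.1, 0.2 and 0.3 SD leave 81%, 68% and 53%. The smaller the observed change, the more a given control change matters.

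**Step 4: precision of the pilot (sampling noise, a separate matter from the bias above).** The inputs are 30 per arm from section 14.3, full retention, and an assumed baseline-to-follow-up correlation ρ. The 95% half-widths, in baseline-SD units, are:

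| Estimate | Formula | ρ = 0.5 | ρ = 0.7 | ρ = 0.8 |
|---|---|---|---|---|
| Change within one arm | 1.96 × √(2(1 − ρ)/30) | 0.36 | 0.28 | 0.23 |
| Between-arm difference in change | 1.96 × √(4(1 − ρ)/30) | 0.51 | 0.39 | 0.32 |
| Between-arm difference, baseline-adjusted | 1.96 × √(2(1 − ρ²)/30) | 0.44 | 0.36 | 0.30 |

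The within-arm interval is the narrowest, but it is an interval for the wrong quantity. Baseline adjustment gives the tighter of the two between-arm intervals. Even that one is too wide to fix a planning effect on its own.

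**The case against.** The strongest reply is that this is a small feasibility study which claims no power, that its secondary aim is only to explore, and that an SAP is foreseen (sections 14.4, 14.5 and 15.1.1). Much of that stands. Descriptive analysis without tests is proper here, and the choice of model and covariates can be left to the SAP. It does not rescue the sentence in 15.1. That sentence leaves nothing about the effect estimate to the SAP, so an SAP with a sound between-arm estimate would still sit beside a protocol that reads change from baseline as caused by drumming.

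A reader might infer more than the text supports:

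- *That the arms are pooled, or that only the intervention arm is summarised.* Section 15.1 says neither. In a parallel-group trial, summaries by arm are the natural reading, but they still need a stated contrast.
- *That randomising controls is wasted.* It is not. Recruitment, retention and data completeness under randomisation are learned whatever is done with the secondary outcomes.
- *That the pilot's point estimate will be the next trial's target difference.* Section 15.1 says only that effect size and variability are for use in power calculations. Carrying the variability forward is sound.
- *That a between-arm difference would cure the unblinded assessment.* It would not, because expectation and rater knowledge differ by arm. The UPDRS is protected by its blinded video rating; the other outcomes are not.

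**Conclusion.** The point holds as a wrong statement in section 15.1: change from baseline is presented as an effect size caused by drumming, and the comparative secondary objective is left without a between-arm estimate. It should be corrected.

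The size depends entirely on how much controls change, which the protocol does not say. Under the assumptions shown (SD of change 1, intervention-arm change 0.5 SD, 90% planned power), control changes of 0.1 to 0.3 SD in the same direction cut the next trial's true power to between 74% and 26%. If controls do not change there is no error, and if they worsen the error reverses. The illustration is in SD units whereas 15.1 specifies percentage change; the need to subtract the control change is the same on either scale.

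The absence of a named covariate set is not itself an error. The primary feasibility outcomes and the progression criteria in section 5.3 are untouched.

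**What to change.** In section 15.1:

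1. State that secondary outcomes are summarised by arm.
2. For each, add the between-arm difference (SParky Samba minus activity as usual) at 12 weeks with its 95% confidence interval, adjusted for baseline score and Hoehn and Yahr stratum, without significance tests. Leave the exact model to the SAP.
3. Delete *drumming-induced*.
4. State that the SD, the baseline-to-follow-up correlation and retention are carried forward to planning, and that the imprecise pilot effect estimate will not by itself set the target difference.
5. Note that the adjusted difference does not remove bias from unblinded assessment of outcomes other than the UPDRS.

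The cost is a few sentences and a little analysis time. Baseline scores and Hoehn and Yahr stage are already collected, so no new data are needed. The one thing given up is quoting the pilot effect as the planning effect.

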15.1.1 Sub-group & Interim Analysis

Exploratory sub-group analyses may be specified in the SAP. No interim analyses are planned.

15.2 Process Evaluation Analysis

Semi-structured interviews will be audio-recorded, transcribed and analysed thematically. All quantitative data will be summarised using frequency based data.

16 Data Management

Source Data is defined as "All information in original records and certified copies of original records of clinical findings, observations or other activities in a clinical trial necessary for the reconstruction and evaluation of the trial. Source data are contained in source documents." There is only one set of source data at any time for any data element.

Source data will be the online versions of the Case Report Forms (CRFs) / Consent form. The preferred option of data collection will be that participants complete the Case Report forms on the REDCap database. However, we will provide paper copies of the CRF forms from the REDCap database to be completed if the participant wishes to complete via this method. Consent will be taken via the e-consent module on REDCap. This will return the consent form to the participant via email.

Access to the database for CTR and the sites will be via username and password and restricted to appropriately trained personnel only.

The database will be housed on local servers managed by Cardiff University staff in accordance with all appropriate legislation.

Identifiable data will be encrypted and stored separately from non-identifiable data. This data will only be made available to those who require it and as part of database testing we will ensure that this data cannot be exported.

Wherever possible, data will be validated at point of entry, thereby reducing the opportunity for missing or unexpected data. All changes made to the data following initial data entry will be recorded and visible via an audit log within the database.

The planning, development, testing and maintenance of the database will be performed in line with CTR SOPs, as will all aspects of the data management function. A data management plan will be developed to outline the details of how data will be collected, transferred stored and accessed by the team.

Trial data						Source	Data				
	eCRF	Participant modical natur	ווובמורמו ווטנכט	Screening Log	Withdrawal form	Electronic System	SAE form	Motor	examination video	MS Teams or	Audio Recordina
Consent						Х					
Concurrent		х									
Medications											
Adverse events		х					х				
Feasibility	х			х	х	х					
outcomes											
Outcome Data	Х										
Adherence Data						х					
UPDRS	х							х			
Process						х					
evaluation											
Questionnaire											
Process										Х	
evaluation											
interview											

16.1 Data Collection

Data will primarily be collected online; however, participants will have an option to complete the data collection with a member of the research team if they don't wish to independently complete it online. Participants will also be offered a phone or video call from a researcher to aid completion of data collection online.

16.2 Completion of Case Report Forms (CRFs)

16.2.1 Electronic CRFs

Participants will be asked to complete CRFS and questionnaire data using an online system. The system will be developed by the CTR and tested prior to going live. The participant can either complete these when at a session or they can be emailed directly to them to complete.

This is a secure encrypted system accessed by an institutional password and complies with the General Data Protection Regulation 2018.

https://redcap.ctr.cardiff.ac.uk/redcap/redcap_v13.7.5/

A user password will be supplied to site staff upon completion of all processes required prior to opening. There access will be restricted to just data collection forms that they need to view, enter and edit.

A detailed data management plan will be developed.

16.2.2 Paper CRFs

We recognise that some aprticipants may struggle to complete questionnaires directly on-line. In addition to the option of facilitatory support from research staff at site, we will also give aprticipants the option of completing PROMs on paper. They can do this as their research visit (aided by research staff if necessary) or at home. If paper versions of the PROMS are completed at site, data will be entered into the REDCap database by local research staff on the trial delegation log. If they request paper versions to be completed at home, these will be sent by CTR trial staff, complete with a stamped addressed envelope for returning completed CRFs to CTR.

17 Protocol/GCP Non-Compliance

The PI should report any non-compliance to the trial protocol or the conditions and principles of GCP to the CTR in writing as soon as they become aware of it.

18 End of Trial Definition

The end of the trial is defined as the date of final data capture to meet the trial endpoints. In this case end of trial is defined as when the last participant has completed their Follow-up interview for the process evaluation- typically by 16 weeks post randomisation.

Sponsor must notify the REC of the end of a clinical trial within 90 days of its completion or within 15 days if the trial is terminated early.

19 Archiving

The TMF and TSF containing essential documents will be archived at an approved external storage facility for a minimum of 15 years. The CTR will archive the TMF and TSFs on behalf of the Sponsor. The Principal Investigator is responsible for archival of the ISF at site on approval from Sponsor. Essential documents pertaining to the trial shall not be destroyed without permission from the Sponsor.

20 Regulatory Considerations

20.1 Ethical & Governance Approval

This protocol has approval from a Research Ethics Committee (REC) that is legally "recognised" by the UK Ethics Committee Authority for review and approval.

This trial protocol has been submitted through the relevant permission system for global governance review in Wales as the lead nation for the trial to the Health Regulatory Authority (HRA).

Approval will be obtained from the host care organisation who will consider local governance requirements and site feasibility. The Research Governance approval of the host care organisation must be obtained before recruitment of participants within that host care organisation.

Participants will not be offered any incentives to join the trial, however all travel costs will be covered for them to attend assessment and intervention sessions.

20.2 Data Protection

The CTR will act to preserve participant confidentiality and will not disclose or reproduce any information by which participants could be identified, except where specific consent is obtained. Data will be stored in a secure manner and will be registered in accordance with the General Data Protection Regulation 2016.

This includes collection of postcode, telephone number and email address to enable contact of participants for follow up and assessment of geographic spread of participants.

20.3 Indemnity

- Non-negligent harm: This trial is an academic, investigator-led and designed trial, coordinated by
 the CTR. The CI, local Investigators and coordinating centre do not hold insurance against claims
 for compensation for injury caused by participation in a clinical trial and they cannot offer any
 indemnity. The Association of the British Pharmaceutical Industry (ABPI) guidelines will not apply.
- Negligent harm: Where studies are carried out in a hospital, the hospital continues to have a duty of care to a participant being treated within the hospital, whether or not the participant is participating in this trial. Cardiff University does not accept liability for any breach in the other hospital's duty of care, or any negligence on the part of employees of hospitals. This applies whether the hospital is an NHS Trust or not. The Sponsor shall indemnify the site against claims arising from the negligent acts and/or omissions of the Sponsor or its employees in connection with the Clinical Trial (including the design of the Protocol to the extent that the Protocol was designed solely by the Sponsor and the Site has adhered to the approved version of the Protocol) save to the extent that any such claim is the result of negligence on the part of the Site or its employees.

All participants will be recruited at NHS sites and therefore the NHS indemnity scheme/NHS professional indemnity will apply with respect to claims arising from harm to participants at site management organisations.

20.4 Trial Sponsorship

Cardiff University will act as Sponsor for trial and the CTR are responsible for coordination of the trial.

Delegated responsibilities will be assigned to staff members at the sites taking part in this trial.

20.5 Funding

The trial has been awarded funding from the Jacques and Gloria Gossweiler Foundation as part of their Research Grants in the field of Neurology. The trial team will report regular updates to the funder including an end of trial report.

21 Trial Management

